7. PROTOCOL DEVIATIONS/VIOLATIONS

The protocol violations and deviations will be identified and assessed by the clinical research physician or designee following company standard operational procedure. Protocol violations and protocol deviations will be summarized for the Enrolled Population.

A by-subject listings of subjects with protocol violations and deviations in the Enrolled Population will be provided.

8. DEMOGRAPHICS AND BASELINE CHARACTERISTICS

The demographics and baseline characteristics will be summarized by dose cohorts in the dose escalation part by selected subgroups in dose expansion part, by selected subgroups at the expanded dose with subjects from both parts, and by study overall for all populations defined in [Section 5.2](#). Individual subject listings for the Enrolled Population will be provided to support the summary tables.

8.1. Demographics

Age (years), height (cm), weight (kg) and Body Mass Index (BMI kg/m²) will be summarized using descriptive statistics (e.g., n, mean, standard deviation, median, minimum, and maximum). Age is calculated based on the date of birth and the date of informed consent (if date of birth is not collected due to country specific regulations, the age recorded in the database will be used, see [Section 17.2](#)). Age category (≤ 65 versus > 65 years), BMI category (< 20 , ≥ 20 to < 25 , ≥ 25 to < 30 and ≥ 30), sex, race, ethnicity and reproductive status (female of child bearing potential, female of non-childbearing potential) will be summarized with frequency tabulations.

BMI = Weight (kg) / (Height (m) x Height (m)).

8.2. Baseline Characteristics

Baseline clinical characteristics include the following parameters:

- Temperature (°C),
- Systolic Blood Pressure (SBP, mmHg),
- Diastolic Blood Pressure (DBP, mmHg),
- Pulse Rate (beats per minute [bpm]),
- ECOG PS
- Evidence of HCC diagnosis (Histological, Clinical and/or Radiologic),
- Barcelona Clinic Liver Cancer (BCLC) staging (B or C),
- Cirrhosis (Yes/No),
- HCC Risk Factor (alcohol, HBV, HCV, non-alcoholic steatohepatitis, unknown or other),
- Child-Pugh score (0-6),
- Baseline AFP level,
- Baseline HBV viral load,
- Baseline HCV viral load,
- Macroscopic Vascular Invasion (Yes/No),
- Extrahepatic Disease (Yes/No), and

- Hepatitis serology (Hepatitis B surface Antigen [HBsAg], Hepatitis B e Antigen [HBeAg], Hepatitis B surface Antibody [HBsAb], Hepatitis B e Antibody [HBeAb], Hepatitis B core Antibody [HBcAb] and/or Hepatitis C Virus Antibody [HCVAb]).

Categorical baseline variables will be summarized using frequency counts and percentage. Continuous baseline variables will be summarized by descriptive statistics in the same way as continuous demographic variables (e.g., n, mean, standard deviation, median, minimum, and maximum). Listings will be presented for the Enrolled Population.

8.3. Medical History

A summary table of medical history with frequency counts and percentage will be presented using Medical Dictionary for Regulatory Affairs® (MedDRA) system and system organ class (SOC) and preferred term (PT) for the Safety Population. Listings will be presented for the Enrolled Population.

8.4. Prior Therapies for This Disease

The number of prior therapies/surgeries will be summarized for prior radiation therapies, prior cancer surgeries, prior systemic anti-cancer therapies, prior hormonal anti-cancer therapies, prior stem cell transplants and prior locoregional therapy for this disease separately and overall by frequency tabulations for the Safety Population. The therapies/surgeries with the same sequence/regimen number are counted as one prior therapy/surgery. Listings of therapies for this disease will also be presented by categories (prior, concomitant, and follow-up) for the Enrolled Population. Prior therapies are the therapies that were started before the first dose of study drug. Concomitant therapies are the therapies that were started on or after the first dose of study drug, but on or before the last dose of study drug. Therapies in the follow-up are the therapies that were started after the last dose of study drug.

[REDACTED]

[REDACTED]

[REDACTED]

[REDACTED]

[REDACTED]

9. STUDY TREATMENTS AND EXTENT OF EXPOSURE

Study treatment and extent of exposure summaries will be provided based on the Safety Population. Descriptive statistics will be provided for treatment duration, number of days dosed, average length of cycle, average number of days dosed per cycle, number of cycles, number of subjects who entered each cycle, actual cumulative dose, average daily dose, actual dose intensity, and relative dose intensity and number of subjects who overdose by dose cohorts in the dose escalation part by selected subgroups in dose expansion part, by selected subgroup at the expanded dose with subjects from both parts, and by study overall.

9.1. Treatment Duration

For each subject and for each study drug, the treatment duration is defined as the length of time elapsed between the first and last non-zero and non-missing study drug dose date and including the duration between planned administration (i.e. rest period for CC-122 and time between last infusion and subsequent planned infusion for Nivolumab). The treatment duration is derived in days which are converted in weeks (by dividing the treatment duration by 7) for the summary.

The first study drug dose date is defined as the earliest date where study drug has been administered (i.e. the drug was administered and the actual dose is not null or zero).

The last study drug dose date is defined as the latest date where study drug has been administered (i.e. the drug was administered and the actual dose is not null or zero).

CC-122 (5/7-day schedule):

CC-122 treatment duration (days) =

$$(\text{Last dose date of CC-122 in the study}) - (\text{First dose date of study drug in the study}) + \text{number of days in drug rest period} + 1.$$

The number of days in rest period to be added is 2 days for 5-days on 2-days off intermittent dose schedule.

Nivolumab:

Nivolumab treatment duration (days) =

$$(\text{Last infusion start date of Nivolumab in the study}) - (\text{first dose date of study drug in the study}) + \text{days covered by last infusion} + 1$$

The days covered by last infusion are 13 days with Nivolumab being administered every 2 weeks (Days 1 and 15).

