4. INVESTIGATIONAL PLAN

4.1. Overall Study Design and Plan

CC-122-HCC-002 is a Phase 1/2 dose escalation and expansion clinical study of CC-122 in combination with Nivolumab in subjects with unresectable HCC who have progressed after or were intolerant to no more than 2 previous systemic therapies for unresectable HCC or are naïve to systemic therapy.

The dose escalation part of the study will explore 1 or more dose levels of CC-122 in combination with Nivolumab using a modified dose escalation (3+3) design (Storer, 1989), followed by an expansion part once the RP2D is defined.

The study is designed to explore three dose levels, to identify the RP2D, and is not required to escalate to a nontolerated dose (NTD) or maximum tolerated dose (MTD). CC-122 will initially be administered orally 5 consecutive days out of 7 (5 days on/2 days off weekly) on Days 1 to 5, 8 to 12, 15 to 19 and 22 to 26 of each 28-day cycle. The investigated starting daily dose of CC-122 will be 2.0 mg, and two subsequent dose levels (3.0 and 4.0 mg) are planned to be evaluated based on evaluation of pre-specified dose limiting toxicities (DLTs). The study intends to identify the RP2D at or below the 4.0 mg dose level, however intermediate dose levels, or a higher dose level, may be evaluated at the discretion of the Safety Review Committee (SRC). Dose escalation to the intermediate or higher dose levels of CC-122 will not exceed 50% of the previously established tolerable dose level. Smaller dose increments based on toxicity, PK profile and pharmacodynamic findings may be evaluated, if necessary. Nivolumab will be administered at the dose of 3.0 mg/kg intravenously (IV) every 2 weeks. Once the RP2D for dosing of CC-122 in combination with Nivolumab is defined, expansion (Phase 2) will start.

A modified 3+3 dose escalation design will be used to identify the initial toxicity of the combination. Up to six subjects will be concurrently enrolled onto a dose level. Decisions as to which dose level to enroll a new subject will be based on the number of subjects enrolled and evaluable, the number of subjects experiencing DLTs, and the number of subjects enrolled but who are not yet evaluable for toxicity in the current cohort at the time of new subject entry.

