5.1.2. General Definitions

General definitions for this study are:

- Where study drug or study treatment is referenced, this refers to Investigational Product (IP): CC-122 or Nivolumab, unless otherwise stated;
- The first dose date refers to the earliest dose of study drug and the last dose date refers to the latest dose of study drug.

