9.9. Relative Dose Intensity

For each subject and for each study drug, the relative dose intensity is defined as actual dose intensity (dose/weeks) divided by expected dose intensity (dose/weeks) and expressed as a percentage. Relative dose intensity will be used for the measurement of study drug compliance.

CC-122:

As per the protocol, the expected dose intensity (dose/week) for each cohort is:

- For dose level -1: 5 mg/week,
- For dose level 1: 10 mg/week,
- For dose level 2: 15mg/week,
- For dose level 3: 20 mg/week.

CC-122 relative dose intensity (%)

$$\frac{\text{CC - 122 actual dose intensity (mg/week)}}{\text{CC - 122 expected dose intensity (mg/week)}} \times 100$$

Nivolumab

As per the protocol, the expected dose intensity (dose/week) for Nivolumab is fixed at 1.5 mg/kg/week.

Nivolumab relative dose intensity (%)

$$\frac{\text{Nivolumab actual dose intensity (mg/kg/week)}}{\text{Nivolumab expected dose intensity (mg/kg/week)}} \times 100$$

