17.2.1. Calculation Using Dates

Calculations using dates (e.g., PFS, subject's age or relative day after the first dose of study drug) will adhere to the following conventions:

- Study days after the start day of study drug will be calculated as the difference between the date of interest and the first date of dosing of study drug plus 1 day. The generalized calculation algorithm for relative day is the following:
 - If TARGET DATE \geq DSTART then STUDY DAY = (TARGET DATE – DSTART) + 1;
 - Else use STUDY DAY = TARGET DATE – DSTART.

Note that Study Day 1 is the first day of treatment of CC-122. Negative study days are reflective of observations obtained during the baseline/screening period. Note: Partial dates for the first study drug are not imputed in general. All effort should be made to avoid incomplete study drug start dates.

- Age (expressed in days) is calculated: AGE = CONSENT – DATE of BIRTH + 1. In practice, age will be transformed to years by dividing the difference by 365.25 days, then truncating.
 - Preference is for using calculated age from clinical database. When not available, calculated age from CRF or IVRS may be used
 - Partial birth date: impute missing day as 15th of the month; impute missing month as July; set missing age for missing year
- Intervals that are presented in weeks will be transformed from days to weeks by using (without truncation) the following conversion formula:
$$\text{WEEKS} = \text{DAYS} / 7$$
- Intervals that are presented in months will be transformed from days to months by using (without truncation) the following conversion formula:
$$\text{MONTHS} = \text{DAYS} / 30.4167$$

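### SAP 9.1 and 9.9 give a CC-122 relative dose intensity below 100% after a mid-week last dose even with no dose missed, and 9.1 leaves unclear when each drug's treatment duration starts

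*SAP*

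**What the plan says.** **End of treatment.** CC-122 is scheduled on "Days 1 to 5, 8 to 12, 15 to 19 and 22 to 26 of each 28-day cycle" (SAP 4.1). The CC-122 duration in SAP 9.1 is the last CC-122 dose date minus a start date, plus rest days, plus 1. On the rest days it says: "The number of days in rest period to be added is 2 days for 5-days on 2-days off intermittent dose schedule". The weekday of the last dose plays no part. For nivolumab, 13 days are added after the last infusion.

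**Start of treatment.** The text of 9.1 opens per drug: "For each subject and for each study drug, the treatment duration is defined as the length of time elapsed between the first and last" administered dose. The start term in the CC-122 formula, however, is "First dose date of study drug in the study", and the nivolumab formula uses the same term. SAP 5.1.2 gives the general meaning: "Where study drug or study treatment is referenced, this refers to Investigational Product (IP): CC-122 or Nivolumab, unless otherwise stated", and "The first dose date refers to the earliest dose of study drug".

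**Use.** Duration in weeks is the denominator of actual dose intensity (9.8). Dividing that by 5, 10, 15 or 20 mg/week, according to dose level, gives relative dose intensity (RDI, 9.9). Section 9.9 adds: "Relative dose intensity will be used for the measurement of study drug compliance". RDI is also printed on the bars of the waterfall plots (10.2).

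**Study day.** SAP 17.2.1 counts study days from the first dosing date of study drug. The same bullet then says: "Note that Study Day 1 is the first day of treatment of CC-122".

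**The concern.** A compliance measure should read 100% for a subject who took every dose that fell due up to the last one. Here it does so only if the last dose is the fifth of a dosing week. A mid-week stop early in treatment is reported as under-dosing that did not occur.

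The start date raises a different problem. The words of 9.1 point to each drug's own first dose, while its formulas, read with 5.1.2, point to the first dose of either drug. Two programmers could produce different exposure tables for any subject whose two drugs did not start together. The note in 17.2.1 adds a third time origin. A subject who received nivolumab first would have events after that infusion on negative study days, which 17.2.1 associates with screening.

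At stake are the exposure and compliance tables and the waterfall annotation. Escalation cohorts are small (decisions at 3 to 6 evaluable subjects, Protocol 7.8), so one subject can move a cohort mean.

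**Working it through.** **Inputs.** Five doses per 7 days (SAP 4.1); duration (9.1); actual dose intensity = cumulative dose / duration in weeks (9.8); expected CC-122 intensity 5, 10, 15 and 20 mg/week and nivolumab 1.5 mg/kg/week (9.9); both drugs planned from Cycle 1 Day 1, with no visit window on that day (Table of Events, footnote b).

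**1. The plan's own figures.** Expected intensity is 5 x dose: 5 x 1.0, 2.0, 3.0 and 4.0 mg = 5, 10, 15 and 20 mg/week. For a full cycle at 2.0 mg with the last dose on Day 26, duration = 26 - 1 + 2 + 1 = 28 days, and 20 x 2.0 = 40 mg over 4 weeks = 10 mg/week, so RDI is 100%. For nivolumab with the last infusion on Day 15, duration = 15 - 1 + 13 + 1 = 28 days, and 6 mg/kg over 4 weeks = 1.5 mg/kg/week, again 100%. The formulas work for completed weeks.

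**2. Mid-week last dose, nothing missed, both drugs from Day 1.** For a last dose on dosing day d of week w:

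- doses = 5(w-1) + d
- duration = 7(w-1) + d + 2 days
- RDI = 7 x doses / (5 x duration) = [35(w-1) + 7d] / [35(w-1) + 5d + 10]

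The dose level cancels. For Day 3 at 2.0 mg: 6 mg / (5/7 week) = 8.4 mg/week, or 84.0% of 10.

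| Last dose | Doses | Duration (days) | RDI (%) |
|---|---|---|---|
| Day 1 | 1 | 3 | 46.7 |
| Day 2 | 2 | 4 | 70.0 |
| Day 3 | 3 | 5 | 84.0 |
| Day 4 | 4 | 6 | 93.3 |
| Day 5 | 5 | 7 | 100 |
| Day 8 | 6 | 10 | 84.0 |
| Day 15 | 11 | 17 | 90.6 |
| Day 22 | 16 | 24 | 93.3 |
| Day 29 | 21 | 31 | 94.8 |
| Day 57 | 41 | 59 | 97.3 |
| Day 169 | 121 | 171 | 99.1 |

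The measure can also rank subjects wrongly. A subject who misses one of the five Week 1 doses and takes the last on Day 5 gets 8 mg over 1 week = 80%. That is above the 70.0% of a subject who took both doses due and stopped on Day 2.

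One subject at 46.7% among others at 100% gives a cohort mean of (46.7 + 200)/3 = 82.2% with 3 subjects, or (46.7 + 500)/6 = 91.1% with 6.

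**3. Later start of one drug, literal formula.** The delays are assumptions; the documents give no frequency. If CC-122 starts s days after nivolumab and every dose is then taken for 4 weeks, RDI = 28/(28 + s): 90.3, 80.0 and 66.7% for s = 3, 7 and 14. If nivolumab starts on Day 8 and is given twice, duration = 22 - 1 + 13 + 1 = 35 days, and 6 mg/kg over 5 weeks = 1.2 mg/kg/week, or 80%. With s = 0 there is no effect. With each drug's own first dose as the start, the 80.0% becomes 100%, but the 46.7% of step 2 remains.

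**4. Candidate corrections for the end effect.**

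- Add the 2 days only after a fifth dose. A Week 1 stop on dosing day k (1 to 4) at 2.0 mg then gives 2k mg / (k/7 week) = 14 mg/week, 140% of expected. A Day 8 stop gives 12 mg / (8/7 week) = 10.5 mg/week, 105%.
- Divide cumulative dose by the dose scheduled from first to last CC-122 dose. A Day 3 stop gives 6/6 = 100%, and so does every row of the table. The subject above who missed one of five doses still gets 8/10 = 80%.

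**The case against.** The convention in 9.1 is stated openly, treats both drugs alike by adding the gap to the next planned administration, and never exceeds 100% for a subject dosed as assigned. A subject who stops on Day 3 did not take the Day 4 and Day 5 doses, so an intensity below 100% is not plainly false. That stands for actual dose intensity, and is a reason to leave 9.1's rest days alone. It does not rescue RDI as a compliance measure. If the untaken Day 4 and Day 5 doses count as missed, compliance is 3/5 = 60%; if not, it is 100%. The reported 84.0% is neither.

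On the start date, 5.1.2 applies only unless otherwise stated, and the per-drug opening of 9.1 may be such a statement. That also stands: this is an ambiguity, not a demonstrated error. A subject who starts CC-122 late has also departed from the planned start, and is fully dosed only from CC-122's own first dose.

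A reader might infer three stronger things that the documents do not support:

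- **That the choice of recommended Phase 2 dose is distorted.** It rests on DLT counts and the Safety Review Committee's review of clinical, PK, pharmacodynamic and laboratory data (Protocol 3.1, 7.8). RDI is not a named criterion, and DLT evaluability uses 75% of planned Cycle 1 doses (Protocol 7.3), not this formula.
- **That about 47% is a typical or overall lower bound.** It is the single-dose extreme of the mid-week effect. Under the literal start date a single CC-122 dose on Day 8 gives 2 mg / (10/7 week) = 1.4 mg/week, or 14.0%.
- **That the rest days should simply be made conditional.** Step 4 shows that this overshoots.

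**Conclusion.** The point holds as a minor correction to descriptive output. The mid-week effect follows directly from 9.1 and 9.9 and is the same at every dose level. It is large only for stops in the first week or two, at most about 5 points after Cycle 1, and under 1 point by Day 169. The late-start effect depends on reading the formula literally with 5.1.2 and vanishes when both drugs start on Cycle 1 Day 1. How often either situation arises cannot be told from the documents.

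The conflict within 17.2.1 is separate from RDI. Its calculation rule agrees with 5.1.2 and with the first-dose origin used for TTP (10.5.2) and for laboratory and vital-sign baselines (17.3). Only the note differs.

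**What to change.** 1. **SAP 9.1:** start the CC-122 formula at the first dose date of CC-122 and the nivolumab formula at the first infusion date of nivolumab. Keep the 2 rest days as they are.
2. **SAP 9.9:** compute CC-122 RDI as cumulative actual dose divided by the planned dose over the scheduled dosing days from first to last CC-122 dose.
3. **SAP 17.2.1:** reconcile the Study Day 1 note with the rest of its bullet and with 5.1.2, using the earliest dose of either drug.

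The cost is a few words in three sections, with no new data. There is a price: CC-122 RDI will no longer equal actual dose intensity divided by a fixed weekly dose, and doses planned after the last one taken will not count as missed. A footnote to the exposure tables and the waterfall plots should say both.

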9.2. Number of Days Dosed

For each subject and for each study drug, the number of days dosed is defined as the total number of days the subjects received a non-zero and non-missing dose.

CC-122 (5/7-day schedule):

CC-122 number of days dosed =

$$\sum \text{days with CC-122 non-missing and CC-122 non-zero dose}$$

Nivolumab:

Nivolumab number of infusions =

$$\sum \text{days with nivolumab non – missing and nivolumab non – zero dose}$$

9.3. Number of Cycles

For each subject and for CC-122, the number of cycles where CC-12 was administered will be summarized.

The number of cycles initiated will be equal to the last cycle number as recorded in the CRF. The number of cycles treated will be equal to the number of cycles dosed.

The detailed calculation of a cycle is described in [Section 17.2.2](#).

9.4. Average Length of Cycle

For each subject and for CC-122, the average length of cycle is defined as the treatment duration in days divided by the number of cycles for each subject.

CC-122:

CC-122 average length of cycle (days) =

$$\frac{\text{CC – 122 treatment duration (days)}}{\text{Number of CC – 122 cycles dosed}}$$

9.5. Average Number of Days Dosed per Cycle

For each subject and for CC-122, the average number of days dosed per cycle is defined as the number of days dosed divided by the number of cycles for each subject; therefore it corresponds to the average number of days the subject was dosed in a cycle.

CC-122:

CC-122 average dose exposure per cycle (mg/cycle) =

$$\frac{\text{CC - 122 number of days dosed}}{\text{Number of CC - 122 cycles}}$$

9.6. Cumulative Actual Dose

For each subject and for each study drug, the cumulative actual dose is defined as the sum of all doses (actual) taken across the treatment period (i.e. across all cycles).

CC-122:

CC-122 cumulative actual dose (mg) =

$$\sum \text{CC - 122 doses}$$

Nivolumab

Nivolumab cumulative actual dose (mg/kg) =

$$\sum \text{nivolumab doses}$$

9.7. Average Daily Dose

For each subject and for CC-122, the average daily dose is defined as the cumulative actual dose divided by the number of days dosed.

CC-122:

CC-122 average daily dose (mg/day) =

$$\frac{\text{CC - 122 cumulative actual dose}}{\text{CC - 122 number of days dosed}}$$

9.8. Actual Dose Intensity

For each subject and for each study drug, the actual dose intensity is defined as the cumulative actual dose divided by the treatment duration (weeks).

CC-122:

CC-122 actual dose intensity (mg/week)=

$$\frac{\text{CC - 122 cumulative actual dose}}{\text{CC - 122 treatment duration (weeks)}}$$

Nivolumab:

Nivolumab actual dose intensity (mg/kg/week) =

$$\frac{\text{Nivolumab cumulative actual dose}}{\text{Nivolumab treatment duration (weeks)}}$$

9.9. Relative Dose Intensity

For each subject and for each study drug, the relative dose intensity is defined as actual dose intensity (dose/weeks) divided by expected dose intensity (dose/weeks) and expressed as a percentage. Relative dose intensity will be used for the measurement of study drug compliance.

CC-122:

As per the protocol, the expected dose intensity (dose/week) for each cohort is:

- For dose level -1: 5 mg/week,
- For dose level 1: 10 mg/week,
- For dose level 2: 15mg/week,
- For dose level 3: 20 mg/week.

CC-122 relative dose intensity (%)

$$\frac{\text{CC - 122 actual dose intensity (mg/week)}}{\text{CC - 122 expected dose intensity (mg/week)}} \times 100$$

Nivolumab

As per the protocol, the expected dose intensity (dose/week) for Nivolumab is fixed at 1.5 mg/kg/week.

Nivolumab relative dose intensity (%)

$$\frac{\text{Nivolumab actual dose intensity (mg/kg/week)}}{\text{Nivolumab expected dose intensity (mg/kg/week)}} \times 100$$

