7.8. Criteria for Dose Escalation

The SRC will make dose escalation decisions. The decision criteria for dose escalation are:

- If no DLT is observed in the first 3 evaluable subjects during the first cycle, dose escalation to the next higher dose level may occur.
- If 1 out of 6 evaluable subjects experiences DLT during the first cycle, dose escalation to the next higher dose level may occur. Additional subjects will be enrolled to expand the cohort to 6 evaluable subjects if less than 6 subjects are evaluable when the DLT is observed.
- If 2 or more out of up to 6 evaluable subjects experience a DLT during the DLT assessment period in a cohort, any further recruitment into that cohort will cease and this dose will be defined as an NTD.
- The SRC will determine if additional subjects will be enrolled in a parallel or at lower dose cohorts to have 6 evaluable subjects in order to define RP2D, or whether an intermediate dose level or an intermittent dosing schedule will be explored in up to 6 newly enrolled subjects. Additional subjects may be added at a given dose level to further assess the safety and/or PK.

Based on above criteria, if no DLT is observed in at least 3 evaluable subjects, the SRC may decide to escalate the dose to the next cohort.

If one DLT occurs prior to a decision by the SRC to dose escalate, the cohort will be expanded to enroll 6 evaluable subjects in total. Subjects 4 to 6 may be enrolled concurrently with the first 3 subjects if complete 28-day toxicity data are not yet available for the first 3 subjects.

If 1 subject out of 6 evaluable subjects experiences a DLT, the dose will be escalated in the next cohort, unless there are other safety considerations by the SRC. The dose may also be declared the RP2D.

The number of cohorts depends on incidence of DLT. A subject may experience more than 1 DLT. Dose escalation decisions are based on the number of subjects experiencing DLT events.

Intra-subject dose escalation beyond the dose initially assigned to a subject is not permitted in Cycle 1. Those continuing to take IP beyond Cycle 1, following approval by the SRC, may have the dose level increased providing the alternative dose level has been shown to be well tolerated by at least one cohort of other subjects in this study.

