7.15. Investigational Product Compliance

Only the pharmacist or the Investigator's designee will dispense CC-122. A record of the number of capsules dispensed to and taken by each subject must be maintained. The pharmacist or the investigator's designee will document the dose dispensed in the appropriate study records. Subjects will use weekly diary cards to record their daily self-administration of CC-122 at home. These will be reviewed by study staff each time the subject visits the clinic. Entries will be clarified, as necessary, so that appropriate information can be captured on the eCRFs. Study site personnel will perform a CC-122 administration compliance check and record this information on the subject's source documentation and on the appropriate eCRF.

Accurate recording of nivolumab IV administration will be made in the appropriate section of the subject's eCRF and source documents. The investigator or designee is responsible for accounting for all study-specific IPs both administered or in their custody during the course of the study.

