9.10. Dose Reduction/Interruption/Delay

For CC-122, dose reduction is defined as a decrease in dose (non-zero) between current and the immediately previous non-missing assigned dose (planned cohort dose level if the first dose) or between assigned dose and actual dose. Total days of dose reduction due to AE include all the days from the start of assigned dose decrease due to AE until either the assigned dose is changed (excluding missing values) or a new (non-missing) reason for assigned dose adjustment is entered, including the days with dose not administered, as well as those days when the actual dose administered is less than the assigned dose due to AE (count only once if redundant with the previous interval). Dose interruption occurs if the dose is not administered except as pre-specified by the protocol (i.e. rest period). If an interruption happens at the start of a cycle and causes a cycle to be postponed, it is also called dose delay. Consecutive doses not administered (including those separated by protocol planned rest period) with the same reason are counted as one interruption. The rest period between two consecutive dose interruptions due to AE will be included in the total days for that dose interruption.

For Nivolumab, a skipped infusion is defined as an infusion that is not administered at all before the subject discontinues from Nivolumab treatment. An incomplete infusion is defined as an infusion for which the actual dose administered is less than the dose assigned.

Dose reduction and interruption will be summarized and summaries will include:

For CC-122

- Frequency count of number of dose reductions;
- Frequency count of number of dose interruptions;
- Reason for dose reduction (including the reason for assigned dose adjustment and the reason for actual dose that is different from assigned dose);
- Reason for dose interruptions;
- Descriptive statistics of time to the first dose reduction (from the first dose);
- Descriptive statistics of time to the first dose reduction (from the first dose) due to an adverse event (AE) for those who have at least one dose reduction due to an AE;
- Descriptive statistics of time to the first dose interruption (from the first dose);

- Descriptive statistics of time to the first dose interruption (from the first dose) due to an AE for those who have at least one dose interruption due to an AE;
- Number and percentage of subjects who have ≥ 7 days of dose interruption due to an AE;

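### SAP 9.9 uses relative dose intensity as the compliance measure, but its fixed cohort denominator misstates CC-122 compliance once the assigned dose changes

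*SAP*

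**What the plan says.** SAP 9.9 defines the measure for each subject and each drug: "the relative dose intensity is defined as actual dose intensity (dose/weeks) divided by expected dose intensity (dose/weeks) and expressed as a percentage". It then gives the measure a second role: "Relative dose intensity will be used for the measurement of study drug compliance".

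The CC-122 denominator is set by cohort: "As per the protocol, the expected dose intensity (dose/week) for each cohort is" 5, 10, 15 and 20 mg/week for dose levels -1, 1, 2 and 3. For nivolumab it is 1.5 mg/kg/week. SAP 5.1.1 groups escalation subjects by the cohort to which they were first assigned. SAP section 9 has no rule that changes the denominator during treatment.

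The numerator (SAP 9.8) is cumulative actual dose over treatment duration in weeks. For CC-122, SAP 9.1 counts days from first to last dose and adds a fixed rest period: "The number of days in rest period to be added is 2 days for 5-days on 2-days off intermittent dose schedule".

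The protocol allows the assigned CC-122 dose to move. Section 7.9 and Table 5 allow up to two reductions, depending on the starting dose, and later re-escalation. Tables 6 and 7 call for holds. After Cycle 1, with approval of the Safety Review Committee, section 7.8 says subjects "may have the dose level increased providing the alternative dose level has been shown to be well tolerated". Nivolumab has no dose reductions (7.9, 7.10.2) but can be withheld (Table 8).

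**The concern.** Compliance asks whether the subject took what was prescribed. Relative dose intensity asks how much drug the subject received compared with the cohort's plan. The two agree only while the prescription equals the plan. After a protocol-directed reduction or hold, a fully adherent subject falls below 100%. After a permitted increase, a subject can miss doses and still reach 100%.

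CC-122 is taken at home and recorded on diary cards (protocol 7.15), so adherence is a fair question to ask of the data. Section 7.8 bases escalation decisions on 3 to 6 evaluable subjects per cohort, so one or two misstated subjects can move a cohort's compliance summary.

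**Working it through.** **Inputs.** CC-122 is given on 5 days of 7, so 20 dosing days per 28-day cycle (protocol 7.2). Dose levels are in protocol Table 4, formulas in SAP 9.1, 9.6, 9.8 and 9.9. Six cycles and the timing of each dose change are my assumptions.

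**The plan's own figures.** 1, 2, 3 and 4 mg × 5 days = 5, 10, 15 and 20 mg/week. Nivolumab is 3.0 mg/kg ÷ 2 weeks = 1.5 mg/kg/week. All reproduce.

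**Formula.** RDI = 100 × [cumulative dose ÷ (duration in days ÷ 7)] ÷ expected weekly dose, where CC-122 duration = last dose date − first dose date + 2 + 1. Over six full cycles the last dose falls on Day 5 × 28 + 26 = 166, so duration = 165 + 3 = 168 days = 24 weeks.

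**No change, none missed, 4 mg.** 120 × 4 = 480 mg; 480 ÷ 24 = 20; 20 ÷ 20 = 100%. The formula behaves correctly when the dose is constant.

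**Dose changes.** The last column is actual dose over assigned dose.

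| Subject | Cumulative dose (mg) | Weekly dose (mg) | RDI | Actual ÷ assigned |
|---|---|---|---|---|
| 3 to 2 mg from Cycle 2, none missed | 20×3 + 100×2 = 260 | 10.83 | 10.83 ÷ 15 = 72.2% | 260 ÷ 260 = 100% |
| 4 to 3 mg from Cycle 2, to 2 mg from Cycle 3, none missed | 20×4 + 20×3 + 80×2 = 300 | 12.5 | 12.5 ÷ 20 = 62.5% | 300 ÷ 300 = 100% |
| 2 to 3 mg from Cycle 3, none missed | 40×2 + 80×3 = 320 | 13.33 | 13.33 ÷ 10 = 133% | 320 ÷ 320 = 100% |
| Same, 25% missed at each dose level | 30×2 + 60×3 = 240 | 10.0 | 10 ÷ 10 = 100% | 240 ÷ 320 = 75% |

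The last row takes the final scheduled dose as taken, so the duration stays at 168 days.

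**Directed holds, no dose change.** A two-week CC-122 hold at 4 mg gives 110 × 4 = 440 mg; 440 ÷ 24 ÷ 20 = 91.7%. One withheld nivolumab infusion of 12 gives 11 × 3 = 33 mg/kg over 11 × 14 + 13 + 1 = 168 days; 33 ÷ 24 ÷ 1.5 = 91.7%.

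**Fixed two-day addition, 2 mg, none missed.** A last dose on Day 1 gives 2 ÷ (3/7) ÷ 10 = 46.7%; on Day 4, 8 ÷ (6/7) ÷ 10 = 93.3%; on Day 5, 10 ÷ (7/7) ÷ 10 = 100%. On the first day of Week 4 (Day 22) it gives 32 ÷ (24/7) ÷ 10 = 93.3%, and on the first day of Week 24, 232 ÷ (164/7) ÷ 10 = 99.0%.

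**The case against.** The best defence is that the rest of SAP section 9 lets a reader separate the causes. It reports number of days dosed, average days dosed per cycle and average daily dose. The 72.2% subject would show 20 days per cycle at 260 ÷ 120 = 2.17 mg/day, which is full adherence at a lower dose. The escalated subject who misses a quarter would show 90 ÷ 6 = 15 days per cycle, not 20. SAP 9.10 adds counts of, and reasons for, reductions and interruptions. This stands. A reader might infer that the sponsor could not tell intolerance from missed capsules; the documents do not support that. The separate summaries are less direct than a ratio, however. Under SAP 9.10, total days of interruption are summarised only for interruptions due to adverse events, and consecutive missed doses with the same reason count as one interruption.

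It also stands that nothing is decided on this figure. No compliance cut-off is defined. Evaluability for dose-limiting toxicity uses its own 75% rule (protocol 7.3), the Efficacy Evaluable population its own 50% rule (SAP 5.2.1), and pharmacokinetics are summarised by actual dose level (SAP 12.1.2). On the waterfall plots (SAP 10.2) relative dose intensity is used properly, as dose intensity.

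Two further inferences are tempting. One is that higher-dose cohorts will look less compliant. The documents give no reduction rates by cohort, and for one reduction from Cycle 2 the same formula gives 79.2% (4 to 3 mg), 72.2% (3 to 2 mg) and 58.3% (2 to 1 mg), so a single step costs the lower cohorts more. The direction is unknown. The other is that the fixed two-day addition is a material bias. It matters only for a mid-week stop very early in treatment.

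None of this makes relative dose intensity a measure of compliance.

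**Conclusion.** The point holds and is minor. If SAP 9.9 is followed as written, the CC-122 compliance figure is wrong for subjects whose assigned dose changes: 72.2% or 62.5% for subjects who took everything, and 100% for one who missed a quarter. Directed holds lower it for both drugs; the dose-change error concerns CC-122 only.

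The sizes rest on six cycles and the assumed timing of changes. They also rest on reading the denominator as that of the initially assigned cohort, which is what SAP 5.1.1 and 9.9 together imply.

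The effect is confined to a descriptive summary. SAP section 15 says the expansion phase will not proceed, which leaves the up to approximately 20 subjects planned for dose escalation (protocol 9.3). Adherence is misstated in the compliance figure and not lost from the report. Relative dose intensity remains a valid exposure measure.

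**What to change.** In SAP 9.9, keep relative dose intensity as an exposure summary and delete the sentence that makes it the compliance measure. Add two definitions:

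- **CC-122 compliance:** cumulative actual dose ÷ cumulative assigned dose from first to last dose, × 100, excluding days on an investigator-directed hold.
- **Nivolumab compliance:** infusions given ÷ infusions planned, × 100, excluding infusions withheld under a directed hold. Without this, deleting the sentence would leave nivolumab with no measure.

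The CC-122 inputs largely exist. SAP 9.10 already defines a reduction by a fall in assigned dose "or between assigned dose and actual dose", so both values are in use. Protocol 7.15 puts diary information and a site compliance check on the eCRF. It also requires: "A record of the number of capsules dispensed to and taken by each subject must be maintained". It does not say that those capsule counts reach the eCRF, so the definition should rest on the dose data and the compliance check, with capsule counts as support.

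The cost is a change of SAP wording, a simple derived ratio for each drug, and one extra exposure row. No new data collection should be needed.
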